Analysis of the primary endpoint of Part 2 will use the logrank test, stratified by randomization strata (fibrosis stage [2 vs 3] and presence or absence of T2DM at Baseline, for a total of 4 strata), to compare the rates in the 2 randomized treatment arms. If multiple adjudicated events are observed in a single subject, only the first observed event will be used in the analysis. The analysis will use the mITT analysis set, with supportive analyses reported for the ITT and PP2 analysis sets. Subjects who do not have an adjudicated event will be censored for analysis at the last recorded study visit. The p-value for the test of no difference between treatment arms (hazard ratio=1) will be presented as well as the hazard ratio from a proportional hazards model (CVC divided by placebo) and corresponding 95% CI. To manifest strong evidence from a single confirmatory study, the hypothesis test of clinical endpoint will be performed at a significance level of 0.00125 (2-sided) if the test of the surrogate endpoint is successful and 0.00005 (2-sided) otherwise. For study success, the hypothesis test of clinical endpoint will be performed at a significance level of 0.05 (2-sided) if the test of the surrogate endpoint is successful and 0.002 (2-sided) otherwise.

Analysis of secondary efficacy endpoints of Part 2 will use similar methods to the primary endpoint analysis in Part 2. The primary endpoint in Part 1, improvement in fibrosis by at least one stage and no worsening of steatohepatitis at Month 12, will be reported for subjects not in the Part 1 analysis (subjects newly randomized in Part 2), and for all subjects in the study (Month 12 results from Part 1 and Part 2 combined). Results for the mITT and PP2 analysis sets will be reported for the secondary endpoints in Part 2. Binary endpoints will be analyzed with the CMH procedure, stratified by randomization strata. Continuous endpoints will be analyzed with analysis of covariance, with randomization strata included as covariates. Time to event endpoints will be analyzed with the stratified logrank test, stratified by randomization strata.

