5.1.1.1 Common Conventions

5.1.1.1.1 Analysis Populations

The analysis populations will consist of subjects as defined below:

Table 5-1 Analysis Populations

Population	Definition	Study Treatment
Screened	All screened subjects who sign informed consent.	—
Intent-to-Treat (ITT)	All randomized subjects will be included in the randomly assigned treatment group, even if they receive a different treatment from that to which they are randomly assigned. This will be a supportive analysis set for selected efficacy analyses. Subjects with missing Screening biopsy data should not be randomized in the study, and hence will not be included in the ITT analysis set, should such subjects exist.	Randomized assignment
Modified Intent-to-Treat (mITT)	All randomized subjects who receive ≥ 1 dose of study drug will be included in the randomly assigned treatment group, even if they receive a different treatment from that to which they are randomly assigned. This will be the primary analysis set for the efficacy analyses.	Randomized assignment
Month 12 per protocol (PP1)	All subjects randomly assigned to a treatment group who have an evaluable biopsy at Screening and another after at least 6 months but before 15 months of follow-up, receive at least 6 months of assigned study drug and have no significant protocol deviations that potentially influence the primary efficacy assessment will be included in the PP1 analysis set. This will be a supportive analysis set for selected efficacy analyses of Part 1 and Part 2.	Randomized assignment

Population	Definition	Study Treatment

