Month 60 per protocol (PP2)	
All subjects randomly assigned to a treatment group who have an evaluable biopsy at Screening, have no significant protocol deviations that potentially influence the primary efficacy assessment, and either:
 
 • Have an adjudicated event that is a component of the primary composite endpoint within 24 months after randomization 
OR
 
 • Have at least 24 months of follow-up for clinical events AND one of the following: 
 • Have an adjudicated event that is a component of the primary composite endpoint within 6 months of last intake of study drug 
OR
 
 • Have a biopsy at least 24 months after randomization and within 6 months of last intake of study drug. 
This will be a supportive analysis set for selected efficacy analyses of Part 2.
	Randomized assignment
Safety	
All subjects who received ≥ 1 dose of study drug will be included in the safety analysis set. Subjects will be included in the treatment group according to actual treatment received, even if they receive a different treatment than that to which they are randomly assigned. Subjects who inadvertently receive both treatments will be included with the CVC group.
 
This will be the primary analysis set for the safety analyses.
	Actual received ¹
Pharmacokinetic	All subjects who are randomized and receive at least one dose of study drug and have at least one post-dose PK sample will be included in the PK analysis set.	Randomized assignment

¹ Subjects will be summarized according to the study treatment received.

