
Part 2: Primary efficacy endpoint (time-to-event)
	
Time-to-event analyses will be performed using the Kaplan-Meier product-limit method with tabular and graphical presentation for the cumulative probability of event rate by treatment group. Subjects will be censored for analysis at the last recorded study visit.
 
Analysis of the primary endpoint of Part 2 will use the logrank test, stratified by true fibrosis stage (2, 3) and T2DM status (presence, absence) at baseline, for a total of 4 strata, to compare the rates in the 2 randomized treatment arms. If multiple adjudicated events are observed in a single subject, only the first observed event will be used in the analysis. The analysis will use the mITT analysis set, with supportive analyses reported for the
	
Same as above
	
Time-to-event KM figure

Type of Endpoint	Description	Timing	Methodology
Part 2 (Global/Region-specific Europe): Testing (primary endpoint) (time-to-event)	
ITT and PP2 analysis sets. Subjects who do not have an adjudicated event will be censored for analysis at the last recorded study visit. The p-value for the test of no difference between treatment arms (hazard ratio=1) will be presented as well as the hazard ratio from a proportional hazards model (CVC divided by placebo) and corresponding 95% CI.
 
Global/Region-specific Europe: To manifest strong evidence from a single confirmatory study, the hypothesis test of clinical endpoint will be performed at a significance level of 0.00125 (2-sided) if the test of the surrogate endpoint is successful and 0.00005 (2-sided) otherwise. For study success, the hypothesis test of clinical endpoint will be performed at a significance level of 0.05 (2-sided) if the test of the surrogate endpoint is successful and 0.002 (2-sided) otherwise.
		
Part 2: Primary efficacy endpoint (sensitivity analyses 1)	The primary endpoint will be performed using the ITT and PP1 populations as sensitivity analyses.	Same as above	Same as above
Part 2: Primary efficacy endpoint (sensitivity analysis 2)	An assessment of primary endpoint will also be made using multiple imputation with informative censoring imputation model. Refer to Section 5.1.1.1.5.	Same as above	Multiple imputation with informative censoring imputation model

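### SAP Table 5-14 names the Month 12 per-protocol set (PP1) for a sensitivity analysis of the Part 2 clinical endpoint, where the same table and the protocol name the Month 60 set (PP2)

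*SAP*

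**What the plan says.** The Part 2 primary endpoint is the time from the Baseline visit to the first adjudicated event (SAP Table 5-13). The documents name analysis sets for it in these places:

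- **SAP Table 5-14, Part 2 sensitivity analyses 1:** "The primary endpoint will be performed using the ITT and PP1 populations as sensitivity analyses".
- **SAP Table 5-14, Part 2 time-to-event entry:** mITT is primary, and the supportive sets are the "ITT and PP2 analysis sets. Subjects who do not have an adjudicated event will be censored for analysis" at the last recorded visit.
- **Protocol 12.3.2.2:** "The analysis will use the mITT analysis set, with supportive analyses reported for the ITT and PP2 analysis sets".

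SAP Table 5-1 defines the two per-protocol sets. PP1, the Month 12 set, needs an evaluable Screening biopsy and "another after at least 6 months but before 15 months of follow-up, receive at least 6 months of assigned study drug", with no significant deviations. PP2, the Month 60 set, is built around the composite endpoint. One way in is this: "Have an adjudicated event that is a component of the primary composite endpoint within 24 months after randomization". The other way is at least 24 months of follow-up plus either an event, or a biopsy taken at 24 months or later, within 6 months of the last study drug intake.

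**The concern.** One table gives two answers to which per-protocol set supports the Part 2 clinical endpoint, and the protocol agrees with only one of them. A programmer cannot tell whether PP1 replaces PP2 or is run beside it.

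PP1 also suits this endpoint poorly. It was built for a single histology reading near Month 12. In a survival analysis clocked from Baseline, a subject must have reached at least Month 6, on drug and able to be biopsied, before being counted, so membership depends on early event-free time. After Month 6, PP1 places no condition on drug intake, although follow-up runs for years. A result labelled per-protocol would be selected on early survival and would not reflect adherence over the period in which most events occur. What is at stake is the reading of one supportive analysis, and a possible dispute after unblinding over which set was prespecified.

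**Working it through.** **1. Sets named, side by side**

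| Place | Endpoint | Sets beside mITT |
|---|---|---|
| Protocol 12.3.2.2 | Part 2 primary | ITT, PP2 |
| SAP Table 5-14, Part 2 time-to-event entry | Part 2 primary | ITT, PP2 |
| SAP Table 5-14, Part 2 sensitivity analyses 1 | Part 2 primary | ITT, PP1 |
| SAP Table 5-14, Part 1 sensitivity analyses 1 | Part 1 primary | ITT, PP1 |
| SAP Table 5-14, Part 2 secondary (binary) | Part 2 secondary | PP2 |
| SAP 5.1.1.3, opening text | primary endpoint, no Part named | ITT, PP1 |

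The Part 2 sensitivity row differs from the Part 1 row by one word of substance. SAP 5.2.2, which lists changes to the planned analyses, records no move from PP2 to PP1. A carry-over is the likeliest explanation, but that is inference. The mismatch stands whatever its cause.

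**2. Who PP1 removes and keeps**

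- A subject who dies before Month 6 cannot have a biopsy at 6 months or later. A subject with an adjudicated liver outcome completes the study at that point (Protocol 7.1), so one whose event falls before Month 6 would also miss the drug and biopsy conditions, apart from cases close to Month 6 where adjudication lags.
- A subject with a non-biopsy event after Month 6 is removed unless a biopsy was obtained in the window.
- A subject whose cirrhosis is found on the Month 12 biopsy stays in, because that biopsy lies inside the window.
- A subject who stops drug at any time after Month 6 can stay in. PP2 ties events that qualify by its second route to the last drug intake.

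**3. Upper bound on events before Month 6**

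Inputs (SAP 5.1.2 and Protocol 12.8.2): placebo 80% event-free at Month 60, hazard ratio 0.62, 1334 CVC and 666 placebo subjects, 367 events. Constant hazards are assumed.

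- Placebo hazard: −ln(0.80)/5 = 0.0446 per year. Median ln 2/0.0446 = 15.5 years (plan: about 15).
- CVC hazard: 0.62 × 0.0446 = 0.0277 per year. Median 25.1 years (plan: about 25).
- Events by Month 6: 1334 × (1 − e^(−0.0277×0.5)) + 666 × (1 − e^(−0.0446×0.5)) = 18.3 + 14.7 = 33.0, and 33.0/367 = 9.0%.

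This counts the whole composite as if every component accrued evenly from day 1, with no dropout. Progression to cirrhosis is seen only on biopsy, and post-baseline biopsies are scheduled at Months 12 and 60 (Protocol 11.2). The plan itself expects many events from the Month 60 biopsy. On these rates, the number observed before Month 6 should therefore be below 33. How far below cannot be said without a split by component.

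**4. Primary test**

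Schoenfeld's formula with 367 events, hazard ratio 0.62 and 2:1 allocation: √(367 × 2/9) × |ln 0.62| = 4.317. Subtracting 3.227 (two-sided 0.00125) gives 86.2% power (plan: 85%). Subtracting 1.960 (two-sided 0.05) gives 99.1% (plan: 99%). The sets named in the sensitivity row do not enter this calculation.

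**The case against.** The best defence is that PP1 is not barred from Part 2. Table 5-1 says of it: "This will be a supportive analysis set for selected efficacy analyses of Part 1 and Part 2". SAP Table 5-5 counts PP1 under the Part 2 analyses, Table 5-7 allows its membership to be updated for Part 2, and the opening of SAP 5.1.1.3 names ITT and PP1 without naming a Part. The row could then be an extra analysis beside PP2. This stands so far: PP1 does have some role in Part 2, most naturally for the Month 12 histology of newly randomized subjects, although the documents do not say so. It does not make PP1 suitable for a time-to-event endpoint clocked from Baseline. Nor does the row read as an addition: it repeats ITT, gives no reason, and has no counterpart in the protocol.

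Three stronger readings are tempting and are not supported:

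- **That the Part 2 per-protocol result is lost.** A reader might infer this from the row alone. The time-to-event entry and Protocol 12.3.2.2 still commit to a PP2 analysis.
- **That 9% to 18% of events would be removed.** The constant hazards give 33 events by Month 6 and 65 by Month 12. The Month 12 figure includes cirrhosis found on biopsies that qualify for PP1. Subjects leaving the study after 6 months of drug should also be biopsied within 30 days, if feasible.
- **That about 19% of subjects would stop drug after Month 6 and still count as per-protocol.** Spreading the 20% overall dropout over 8 years gives such a figure, but that 20% is a dropout allowance in the event calculation. The protocol treats stopping drug separately from leaving the study, and the documents give no rate for stopping drug.

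**Conclusion.** The inconsistency is real: one row names PP1 where the same table and the protocol name PP2 for the same endpoint. PP1 is the wrong kind of set for that endpoint because it conditions on early event-free time and ignores later stopping of drug. The direction of the problem follows from the definitions; its size cannot be derived from the documents. About 33 events (9% of 367) is an upper bound for the first 6 months only, and it rests on constant hazards at the planning rates. The consequence is confined to a supportive analysis and does not touch the mITT primary test, alpha or power. The correction is worth making because the row, followed as written, yields a mis-specified analysis.

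A reader might also infer that PP2 should be redefined, since its membership depends partly on outcome. That is a separate question and is not needed to resolve this one.

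**What to change.** In SAP Table 5-14, Part 2 sensitivity analyses 1, replace PP1 with PP2, so that the row matches the time-to-event entry and Protocol 12.3.2.2. In the opening text of SAP 5.1.1.3, state that the ITT and PP1 sensitivity analyses apply to the Part 1 primary endpoint. If a PP1 analysis of the clinical endpoint was intended as an addition, the SAP should say so and give the reason.

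The cost is one changed term and one clarifying phrase in an SAP amendment before the Part 2 database lock. The protocol, data collection and sample size do not change. The corrected row will restate the supportive analyses already listed in the time-to-event entry, which does no harm.

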### **12.8.2. Part 2**

The sample size for the primary endpoint analysis in Part 2 is based on the estimated event-free survival rate of 80% for the placebo group and detection of a hazard ratio of 0.62 by the end of the study (corresponding to a median event-free survival time of approximately 15 years for placebo and 25 years for CVC). A total of 2000 subjects (2:1 randomization ratio between CVC and placebo) enrolled approximately uniformly over 2 years for an overall study duration of approximately 8 years (2 years of accrual period plus 5 to 6 years of follow-up) will lead to about 367 events, after accounting for an overall dropout rate of 20%. With these events, there will be 85% power to demonstrate strong evidence of superiority of CVC over placebo (at a 2-sided 0.00125 significance level, for a single registration study), and 99% power to test the superiority of CVC over placebo (at the 2-sided test 0.05 significance level for a registration study). EAST 6.4 is used for the calculation.

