Responder	
 • Categorical descriptive statistics for responders and nonresponders 
 ○ Nonresponders include: 
 ▪ Subjects who do not meet responder criteria ▪ Subjects missing the post-baseline liver biopsy will be included as nonresponders (see Section 5.1.1.1.5 for handling of missing biopsy or inadequate biopsy) • Risk differences and Wilson's method for CIs vs Placebo • Estimates derived from Cochran-Mantel-Haenszel (CMH) model controlling for factors (treatment group, fibrosis stage at baseline [2 vs 3] and presence or absence of T2DM at baseline) 
 ○ Mantel-Haenszel (MH) odds ratios (ORs) and 95% CIs vs Placebo ○ P-values comparing treatment group vs Placebo • N1 = all subjects unless otherwise specified
Time-to-event (TTE)	
 • Categorical descriptive statistics for subjects with events and censoring 
 ○ Censoring includes: 
 ▪ Subjects who do not meet event criteria ▪ Subjects with no post-baseline values of corresponding parameters • Quartiles, estimated event rates, and CIs derived from Kaplan-Meier (KM) nonparametric model using log-log transformation of survival function using product-limit method • Estimates derived from Cox proportional hazards model controlling for factors (treatment group, fibrosis stage at baseline [2 vs 3] and presence or absence of T2DM at baseline) 
 ○ Hazard ratios (HRs) and CIs vs Placebo • Estimates derived from stratified log-rank model controlling for factors (treatment group, fibrosis stage at baseline [2 vs 3] and presence or absence of T2DM at baseline) 
 ○ P-values comparing treatment group vs Placebo • N1 = all subjects unless otherwise specified

Methodology	Description
KM figure	
 Step-function figure of cumulative distribution function [1 - survival function] estimates with censoring indicators, derived from KM nonparametric model

CFB = change from baseline; ANCOVA = analysis of covariance; TTE = time-to-event.

Raw and derived data listings will be provided, and will be fully defined in the table, figure, and data listing specification document.

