Time-to-event (Part 2: primary endpoint)	Treatment Period	
 All subjects in mITT analysis set included. Any available adequate liver biopsy after baseline will be used for assessment of components of the clinical endpoint that require a biopsy, no matter when obtained. Subjects with multiple liver biopsies will be included as an event if any (one or more) biopsy meets the definition of the primary endpoint, as determined by the adjudication committee. Subjects who do not have an evaluable liver biopsy at both Screening and post-baseline will be included in the analyses as having an event only if they meet a component that does not require a biopsy; otherwise they will be included as not having an event and censored at the last visit. Subjects with partial follow-up data will be included as an event if they meet the criteria for any component of the primary efficacy endpoint, and as a nonevent if they do not meet the criteria for any component. A sensitivity analysis assuming data are missing not at random will be reported. An additional sensitivity analysis imputing an event at the time of censoring will also be reported, although it is anticipated that this analysis will not be informative unless many subjects discontinue due to unobserved NASH progression, which cannot be known.
CFB ANCOVA	Months 6 and 12 in Part 1, and Month 12 and annually thereafter in Part 2 (Month 6 in Part 2 for some endpoints)	
 If missing covariates (including baseline if applicable) 
 Subject excluded Observed data for mean absolute change and relative change from baseline to the times specified in the endpoints will be analyzed. There is no imputation for missing data.
Multiple imputation (Part 1: primary efficacy endpoint)	Month 12 MAR and MNAR	
A sensitivity analysis for the primary efficacy analysis in Part 1 will use multiple imputation to investigate the impact of missing data under a Missing At Random (MAR) assumption. For this analysis, the Month 12 biopsy results will be imputed for the subjects who do not have an evaluable biopsy after baseline. The imputation model will be defined before Part 1 unblinding to avoid the addition bias.
 
The multiple imputation model will use the MI procedure in SAS, using code such as the following:
 <pre>proc mi data=<inputdsn> seed=1305417 nimpute=100 out=<outputdsn>; class outcome trt; var trt <explanatory> outcome;</pre>

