
Part 2: Primary efficacy endpoint (binary responder definition)
	
The proportion of subjects with adjudicated clinical endpoints for Part 2, along with each component of the endpoint, will be summarized by treatment group.
 
For the primary efficacy analysis in Part 2 using the mITT analysis set, any available liver biopsy after baseline will be used for assessment of components of the clinical endpoint that require a biopsy, no matter when obtained. Subjects who do not have an evaluable liver biopsy at both Screening and post-baseline will be included in the analyses as having an event only if they meet a component that does not require a biopsy; otherwise they will be included as not having an event and censored at the last visit. Subjects with multiple liver biopsies will be included as an event if any (one or more) biopsy meets the definition of the primary endpoint, as determined by the adjudication committee.
 
Two-sided 95% CIs for the proportion of subjects who meet the primary efficacy endpoint, calculated using Wilson’s method for CI, will be reported.
	
The primary analysis for Part 2 will occur when adjudicated events have been accrued in approximately 367 unique subjects. Because many events may be observed from the Month 60 liver biopsy, and given that all reported events will need to undergo independent adjudication, it is possible that a different number of subjects with events will be included in the analysis. All subjects and events in the database at the time of Part 2 database lock and unblinding will be included in the primary analysis of Part 2. If multiple events are observed in a single subject, only the first observed event will be used in the analysis.
	
Responder
 
Two-sided 95% CIs for responder using Wilson’s method for CI.

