Part 2: Primary efficacy endpoint (sensitivity analysis 3)	Analysis of the primary endpoints for Part 2 will also use the Cochran-Mantel-Haenszel (CMH) test, stratified by true fibrosis stage (2, 3) and T2DM status (presence, absence) at baseline, for a total of 4 strata, to compare the event rates in the 2 randomized treatment arms.	Same as above	Cochran-Mantel-Haenszel (CMH) test, stratified by true fibrosis stage (2, 3) and T2DM status (presence, absence) at baseline
Part 2: Primary efficacy endpoint (sensitivity analysis 4)	An assessment of primary endpoint will also be made using imputation of subjects censored without an event before 5 years of follow-up	Same as above	Time-to-event Logrank test

Type of Endpoint	Description	Timing	Methodology
Part 2: Secondary efficacy endpoints (binary)	
Analysis of secondary efficacy endpoints of Part 2 will use similar methods to the primary endpoint analysis in Part 2. The primary endpoint in Part 1, improvement in fibrosis by at least one stage and no worsening of steatohepatitis at Month 12, will be reported for subjects not in the Part 1 analysis (subjects newly randomized in Part 2), and for all subjects in the study (Month 12 results from Part 1 and Part 2 combined).
 
Results for the mITT and PP2 analysis sets will be reported for the secondary endpoints in Part 2. Binary endpoints will be analyzed with the CMH procedure, stratified by true fibrosis stage (2, 3) and T2DM status (presence, absence) at baseline.
	Same as above	Cochran-Mantel-Haenszel (CMH) test, stratified by true fibrosis stage (2, 3) and T2DM status (presence, absence) at baseline

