The sample size for the primary endpoint analysis in Part 2 is based on the estimated event-free survival rate of 80% for the placebo group and detection of a hazard ratio of 0.62 by the anticipated end of the study at Month 60 (corresponding to a median event-free survival time of approximately 15 years for placebo and 25 years for CVC). A total of 2000 subjects (2:1 randomization ratio between CVC and placebo) enrolled approximately uniformly over 2 years for an overall study duration of approximately 8 years (2 years of accrual period plus 5 to 6 years of follow-up) will lead to about 367 events, after accounting for an overall dropout rate of 20%. With these events, there will be 85% power to demonstrate strong evidence of superiority of CVC over placebo (at a 2-sided 0.00125 significance level, for a single registration study), and 99% power to test the superiority of CVC over placebo (at the 2-sided test 0.05 significance level for a registration study).

EAST 6.4 is used for the calculation.

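### Part 2 sensitivity analysis 3 compares crude event proportions and ignores time at risk, so unequal withdrawal biases it toward the arm that loses more subjects

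*SAP*

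**What the plan says.** The primary Part 2 analysis uses follow-up time: "Analysis of the primary endpoint of Part 2 will use the logrank test", stratified by fibrosis stage and diabetes status, with event-free subjects censored at their last visit (SAP Table 5-14; Protocol 12.3.2.2).

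Sensitivity analysis 3 in the same table does not: "Analysis of the primary endpoints for Part 2 will also use the Cochran-Mantel-Haenszel (CMH) test". It applies that test over the same four strata "to compare the event rates in the 2 randomized treatment arms". It sets no denominator or missing-data rule of its own, so the general rules apply. The responder method in SAP Table 5-2 has "N1 = all subjects unless otherwise specified". SAP Table 5-4, for the Part 2 primary endpoint, takes subjects with partial follow-up as an event if they meet a component, "and as a nonevent if they do not meet the criteria for any component".

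The table also plans a description of the same crude figures: "The proportion of subjects with adjudicated clinical endpoints for Part 2, along with each component of the endpoint, will be summarized by treatment group", with Wilson intervals.

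On losses, Protocol 12.8.2 says that 2000 subjects "will lead to about 367 events, after accounting for an overall dropout rate of 20" per cent. Neither document splits that figure by arm.

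**The concern.** A subject who leaves after one event-free year and a subject followed event-free to the end contribute the same nonevent to the CMH table. The arm that loses more subjects has less time in which events can be seen, so it shows a lower proportion even when the hazards are equal. The log-rank test removes such subjects from the risk set when they leave; the CMH comparison in effect assumes that they stayed event-free.

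A sensitivity analysis of a long outcome trial should show whether the result is robust to incomplete follow-up. This one is distorted by incomplete follow-up, and its p-value will stand beside the log-rank as support. It could agree or disagree with the primary result for reasons unrelated to treatment.

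**Working it through.** **Inputs.** From SAP 5.1.2 and Protocol 12.8.2: "estimated event-free survival rate of 80% for the placebo group" at Month 60; hazard ratio 0.62; 2:1 allocation; 2 years of uniform accrual; about 8 years in all; about 367 events; 20% dropout overall. Arm sizes are 1334 and 666. Withdrawal rates by arm are my assumptions.

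**The plan's own figures.** Power = Φ(√(367 × 2/3 × 1/3) × |ln 0.62| − z) = Φ(9.031 × 0.478 − z). With z = 3.227 (two-sided 0.00125) this is 86.2%, against 85% stated. With z = 1.960 it is 99.1%, against 99% stated. At 8 years with 20% dropout, exponential hazards give 357 to 377 events, depending on when the 20% is reached. The plan's figures reproduce.

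**Null case.** Let both arms have hazard λ = −ln(0.8)/5 = 0.0446 per year, let withdrawal be exponential at rate δ, and put h = λ + δ. For a stop at time T, the expected crude proportion with an event is

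P = (λ/h) × [1 − (e^(−h(T−2)) − e^(−hT)) / (2h)].

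T must match the stopping rule. At a fixed 8 years, the 4% v 2% case would give 481 events, well beyond the target. Solving 1334·P(CVC) + 666·P(placebo) = 367 gives T = 5.97 years. Then:

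- CVC, h = 0.0846: P = 18.06%.
- Placebo, h = 0.0646: P = 18.93%.
- Check: 1334 × 0.1806 + 666 × 0.1893 = 241 + 126 = 367.
- Difference −0.0087. Pooled SE = √(0.1835 × 0.8165 × (1/1334 + 1/666)) = 0.01837. Unpooled SE = 0.01848.
- Significant for CVC: Φ((−1.96 × 0.01837 + 0.0087)/0.01848) = Φ(−1.48) = 7.0%.
- Significant for placebo: 0.8%. Total 7.8%.

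| Withdrawal per year, CVC v placebo | Overall withdrawal by 7 years | Two-sided 5% rejection, stop at 367 events | Same, fixed 8 years |
|---|---|---|---|
| 3% v 3% | 18.9% | 5.0% | 5.0% |
| 4% v 2% | 20.6% | 7.8% | 12.2% |
| 5% v 2.5% | 25.0% | 9.4% | 15.8% |
| 8% v 4% | 36.7% | 17.8% | 29.0% |

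Overall withdrawal is 1 − (1334·e^(−7δ) for CVC + 666·e^(−7δ) for placebo)/2000; 7 years is the mean follow-up of an 8-year study. The plan does not say when its 20% is reached. At the shorter mean follow-up of a null trial stopped at 367 events (5.09 years for the third row), that row would be about 19%.

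**Cross-check by simulation** (HR 1, four strata, 2000 trials). Withdrawal by Month 60 was 20% on placebo and 30% on CVC:

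- Fixed 8 years: CMH rejects 14.9%, the stratified log-rank on the same data 4.4%.
- Stopped at 367 events: CMH 9.7%, log-rank 5.1%.
- Reversed (30% placebo, 20% CVC, 8 years): CMH rejects 15.3%, almost all against CVC.
- Equal 20% withdrawal: CMH rejects 4.9%.

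Entry was staggered in every run, so the equal-withdrawal result shows that staggered entry alone does no harm. With equal withdrawal and HR 0.62, CMH has 88.3% power at 0.00125 against 89.7% for log-rank, so it adds little even when valid.

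**The case against.** **No decision rests on it.** Alpha attaches to the clinical-endpoint test described with the log-rank (SAP Table 5-14 and 5.1.1.3.3). A reader might infer that type I error is inflated or that a false claim could be confirmed. The documents do not support that: false confirmation needs the log-rank to reject as well. In simulated null trials, joint rejection favouring CVC was 2.5% to 3.1%, the log-rank's own rate. What is lost is the value of the check. This objection stands.

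**The size depends on assumptions.** A reader might take 12% to 29% as the error rate. Those figures ignore the event-driven stop, and on the 7-year reckoning the larger cases exceed the planned 20% dropout. A reader might also infer that CVC subjects will leave more often, from the Phase 2b Year 2 discontinuations for adverse events (3.4%, 1.4% and 0; Protocol 5.3.3). Those are 5, 1 and 0 subjects, and stopping drug is not leaving the study. Off-drug follow-up is encouraged, a biopsy is sought at withdrawal after 6 months on drug where feasible, and survival is collected for everyone. My model credits none of this recovery. In the other direction, the bias grows if many events surface only at the Month 60 biopsy and are missed by those who leave sooner.

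**Censoring is probed elsewhere.** Sensitivity analysis 2 models informative censoring, analysis 4 imputes for subjects censored before 5 years, and a further analysis imputes an event at censoring. These are useful, but they do not correct analysis 3.

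**The Wilson intervals are descriptive** and sit beside planned Kaplan-Meier estimates. They need not be removed.

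**Conclusion.** The point holds as a defect in one supportive analysis. By construction, sensitivity analysis 3 favours whichever arm loses more subjects. Under the one scenario that fits 20% dropout at 7 years with a 2:1 ratio of withdrawal rates, its two-sided error at 5% is about 7.8% rather than 5%, with 7.0% rather than 2.5% favouring CVC. With equal withdrawal there is no bias; with more withdrawal on placebo the bias runs against CVC. The figures assume exponential, non-informative withdrawal, no recovery of events after withdrawal, and by-arm rates that the documents do not give. The primary conclusion is not threatened. The change is worth making because it is cheap and removes a misleading p-value.

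**What to change.** Before database lock, do one of the following.

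- Replace sensitivity analysis 3 with a stratified difference in Kaplan-Meier event probability at one fixed time just after the Month 60 biopsy window, with Greenwood variance and the same four strata.
- Keep the CMH comparison but label it descriptive, with no supportive p-value.

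In either case, keep crude counts and Wilson intervals as description beside the planned Kaplan-Meier estimates, and report withdrawal and follow-up time by arm so that a reader can judge any imbalance.

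The cost is a few lines of SAP text and programming. The fixed-time comparison has two limits: it does not use later events, and, like the log-rank, it assumes non-informative censoring. Sensitivity analysis 2 and the event-at-censoring imputation already probe that assumption and should stay.
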